7.7 PATIENT-REPORTED OUTCOMES

The following questionnaires will be used to evaluate general and disease and diseasespecific quality of life, and device usability.

Type 1-Diabetes Distress Scale (T1-DDS)

The T1-DDS is a 28-item self-report instrument. Each item is rated on a 6-point scale from (1) "not a problem" to (6) "a very serious problem." The scale yields an overall distress score based on average responses along the 1-6 scale for all 28 items (range = 1-6). The

scale also yields a score for each of seven subscales based on the average response on all of the items in that subscale (range = 1-6).

Hypoglycemia Confidence Scale (HCS)

The HCS is a nine-item self-report scale that examines the degree to which people with diabetes feel able, secure, and comfortable regarding their ability to stay safe from hypoglycemic-related problems. Each item is rated on a 4-point scale from (1) "not confident at all" to (4) "very confident". The total score is calculated as the sum of each item divided by the number of items completed.

Diabetes Quality of Life-brief (DQOL-brief)

The DQOL-brief is a 15-item instrument that provides a total quality-of-life score. Each item is rated on a 5-point scale from (1) "Very Dissatisfied" or "All the Time" to (5) "Very Satisfied" or "Never." Respondents must answer at least ten (two thirds) questions to be included in the analysis. The DQOL total score is calculated by summing the scores for all items and dividing by the numbers of responses answered. Higher scores indicate a more positive quality of life.

Clarke Hypoglycemia Awareness

Clarke Questionnaire is an eight-item questionnaire to assess reduced awareness of hypoglycemia. Responses to each item are scored as "A" or "R" (or "U" which is equal to four "R" responses). Total of four or more "R" responses are considered to indicate reduced awareness. Generally, no missing data imputation will be performed, but it is possible in certain cases to determine whether or not a participant has reduced awareness, even in the presence of missing responses (e.g., participant is missing a single response, but if the participant only has two "R" responses for the remaining seven items, it can be concluded that the participant does not have reduced awareness since adding another "R" response would result in fewer than four "R"s).

EQ-5D-3L

The EQ-5D-3L is a short, generic, validated quality-of-life instrument used to measure health outcomes. It consists of five dimensions (questions) regarding mobility, self-care, usual activities, pain/discomfort and anxiety/depression, and one visual analog scale to measure the participant's self-rated health. Each of the five dimensions is divided into three levels of perceived problems: Level 1 indicating no problem, Level 2 indicating some problems, and Level 3 indicating extreme problems. Responses to five dimensions can be converted into a single summary index score.

The EQ VAS records the participant's self-rated health on a 0 to 100 scale. Missing values in the EQ VAS should be coded as "999" and ambiguous values (e.g., the line crosses the scale twice) should be treated as missing values.

As the study is conducted in US and France, the US participants will be analyzed based on US value set, and the France participants will be analyzed based on France value set.

DAWN Impact of Diabetes Profile (DIDP)

The DIDP is a six-item questionnaire soliciting responses regarding the impact of diabetes on certain aspects of life. Seven response options range from left to right as "Very negative impact" (score=7) to "Very positive impact" (score=1). Response option "Not Applicable" will be treated as missing. Up to two missing or "N/A" responses can be tolerated. Item scores can be reported independently. The composite score is calculated by summing individual items and diving by the number of completed items (therefore, excluding "N/A" or missing responses). The composite score is converted into a percentage score by subtracting 1 from the composite score, dividing by 6, and multiplying by 100. Lower scores indicate greater positive impact across different aspects.

Pittsburgh Sleep Quality Index (PSQI)

The PSQI is used to measure the quality and patterns of sleep, by measuring seven domains: subjective sleep quality, sleep latency, sleep duration, habitual sleep efficiency, sleep disturbances, use of sleep medication, and daytime dysfunction over the last month. Responses are converted to a 0 to 3 scale, with higher scores indicating more negative quality of sleep. A global sum of \geq 5 indicates a "poor" sleeper. The PSQI global score is calculated as the sum of the seven component scores.

System Usability Scale (SUS)

The SUS is a 10-item questionnaire constructed on a 5-point Likert scale, with responses ranging from (1) "Strongly disagree" to (5) "Strongly agree". It is not recommended that the individual items be scored, but rather a single composite measure of the overall usability of the system should be reported. The SUS score ranges from 0 to 100, and is calculated as follows:

- 1. For items 1, 3, 5, 7, and 9, subtract 1 from the reported score
- 2. For items 2, 4, 6, 8, and 10, the contribution equals 5 minus the reported score
- 3. Sum the contributions (each will range from 0 to 4), multiply by 2.5

Insulin Dosing Systems: Perceptions, Ideas, Reflections, and Expectations (INSPIRE)

The INSPIRE for adults is a 22-item validated questionnaire to evaluate the impact of automated insulin dosing (AID) systems on the psychosocial functioning and quality of life (QoL) of individuals with Type 1 diabetes. Each item is rated on a six-point scale, from strongly disagree (score=0) or not applicable, to strongly agree (score=4). Mean score is calculated based on answered responses, then multiplied by 25. The final score will range from 0 to 100, with higher scores indicating more positive appraisal of the AID.

For validated questionnaires, the prescribed scoring algorithm will be followed. The results will be presented using summary statistics. Scores will be compared between treatment groups using the same methods described above for the secondary and exploratory endpoints.

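### The SAP's worked example for a missing Clarke item rules out reduced awareness without allowing for a U response, which by the SAP's own scoring would cross the cut-off

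*SAP*

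**What the plan says.** The Clarke paragraph of SAP section 7.7 gives four pieces of scoring information.

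- **Length.** "Clarke Questionnaire is an eight-item questionnaire to assess reduced awareness of hypoglycemia".
- **Weights.** Each item is scored A or R, with U as a further possibility "which is equal to four" R responses.
- **Cut-off.** "Total of four or more 'R' responses are considered to indicate reduced awareness".
- **Missing items.** "Generally, no missing data imputation will be performed, but it is possible in certain cases to determine whether or not a participant has reduced awareness". This is followed by a worked example in parentheses: one response is missing and two of the other seven are R. The SAP says that "it can be concluded that the participant does not have reduced awareness", and gives as its reason "since adding another 'R' response would result in fewer than four 'R's".

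Neither the SAP nor the protocol lists the Clarke items, says which of them can be scored U, or limits the example to a missing item that cannot be U.

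Clarke is collected at Visit 2 and again at Visit 8 or early withdrawal (protocol Table 2). The end of SAP section 7.7 says that questionnaire scores will be compared between groups by the methods used for the secondary and exploratory endpoints.

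**The concern.** The example is offered as a deduction: the missing item is said to be unable to change the answer. A deduction of that kind has to hold for the worst response that the missing item could have had. By the SAP's own weights the worst response is U, not R, and the example does not consider it.

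What is at stake is the classification of participants with an unanswered Clarke item. SAP section 5.2.6 analyses exploratory binary endpoints on complete cases. If Clarke status is handled that way, a participant whose status is unknown would enter the analysis as an observed case of preserved awareness instead of being left out. The example is also the only operational guidance on missing Clarke items, so a programmer is likely to extend its logic to other patterns of missing responses.

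**Working it through.** **Inputs, all from SAP section 7.7**

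- Eight items, of which seven are answered and one is missing in the example.
- Weights in R-equivalents: A = 0, R = 1, U = 4.
- Observed count in the example: r = 2.
- Reduced awareness if the total is 4 or more.

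**Formula.** Total = r + weight of the missing item.

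**Step 1. The SAP's own figure.** With the missing item taken as R, 2 + 1 = 3, which is below 4. The SAP's sum is correct for that case.

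**Step 2. All responses that the SAP's scoring allows for the missing item.**

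| Missing item | Total | Status |
|---|---|---|
| A | 2 + 0 = 2 | not reduced |
| R | 2 + 1 = 3 | not reduced |
| U | 2 + 4 = 6 | reduced |

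The totals fall on both sides of 4, so the status is undetermined unless U can be ruled out for that item.

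**Step 3. Every observed count with one item missing.**

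| Observed count r | Missing item can be A or R only | Missing item can also be U |
|---|---|---|
| 0 | 0 to 1: not reduced | up to 4: undetermined |
| 1 | 1 to 2: not reduced | up to 5: undetermined |
| 2 (SAP example) | 2 to 3: not reduced | up to 6: undetermined |
| 3 | 3 to 4: undetermined | up to 7: undetermined |
| 4 or more | reduced | reduced |

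Where the missing item can be U, even an observed count of zero does not settle the matter, because 0 + 4 = 4 meets the cut-off. Only an observed count of four or more is determinate, and then as reduced awareness.

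**Step 4. Direction of error.** The example assigns only one label, not reduced. That label is right if the missing item would have been A or R and wrong if it would have been U. Any error from the example therefore moves a participant from reduced to not reduced.

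**The case against.** The strongest reply has four parts.

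**It is an illustration.** The governing principle is that missing items are generally not imputed and that status is assigned only where it can be determined. That principle is sound, and it is the one that the fix below makes explicit. This stands as to weight: what is defective is one example, not the principle. It does not save the example, which applies the principle incorrectly and is the only case shown.

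**Scoring is also governed elsewhere.** SAP section 7.7 ends by saying that validated questionnaires follow their prescribed algorithm. Protocol section 12.6 says that scoring follows the guidelines and that scores missing through unanswered questions are not imputed. These show that the example is not the sole instruction. They do not cancel it: a general sentence does not displace a specific worked case in the same section, and the SAP prevails over the protocol where the two differ (SAP section 1, protocol section 12.7).

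**U may be possible for only some items.** If so, the example is correct for the remaining items. If every item could be U, the example could never be correct. The documents do not say which holds, so how often the problem arises cannot be settled from them. The condition still has to be stated.

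**The consequence is small.** This stands in full. Clarke is not a primary or secondary endpoint and is not in the testing hierarchy. Protocol section 11.4 treats outcomes outside the listed endpoints as exploratory, and SAP section 5.2.6 says that exploratory results will not support clinical claims.

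A reader might also infer three stronger points that the documents do not support:

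- *That everyone who fits the example is misclassified.* Only those whose unanswered item would have been U are.
- *That the problem falls on people who skip the most serious item.* The documents neither list the items nor rank them, and the example covers a missing response to any of the eight.
- *That the comparison between groups is biased.* The same scoring applies in both arms, and nothing in the documents points to a difference between arms in missing Clarke items.

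**Conclusion.** The worked example is an invalid deduction under the SAP's own scoring. With two R and one item missing, the possible totals are 2, 3 or 6 against a cut-off of 4. Preserved awareness can be concluded only if the missing item cannot be scored U. Where the item would have been U, the example labels a participant with reduced awareness as not reduced, and it cannot err in the other direction.

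This rests on the weights and cut-off in SAP section 7.7, and on the absence from both documents of any restriction on which items can be U. The number of participants affected is not given. It is probably small, because it requires an unanswered item that would have been U and too few R among the answered items to reach the cut-off. No primary or secondary conclusion changes. This is a minor correction, worth making because it is cheap and because the error runs towards the favorable category on a measure of hypoglycemia awareness.

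**What to change.** Correct the example in SAP section 7.7 and state the general condition behind it. Take r as the observed count in R-equivalents. The best case for the missing items adds 0. The worst case adds four for each missing item that the instrument's scoring key allows to be U, and one for each of the others.

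- **Reduced awareness** if r is already 4 or more.
- **Not reduced** if r plus the worst case is below 4. This requires that none of the missing items can be U.
- **Missing** in all other cases.

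State from the scoring key which items can be U, since the rule cannot be programmed without that list. The present example can stay if it is limited to a missing item that cannot be U.

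The cost is a short SAP edit and a few more participants with missing Clarke status. No new data are needed, and no other endpoint is affected.

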7.8 OTHER DATA SUMMARIES

The distribution of each baseline characteristic or demographic parameter of interest (such as age, gender, medical history, etc.) will be presented. Data on all enrolled participants and participants included in mITT analysis set will be presented. Continuous variables will be summarized using count, mean, median, standard deviation, and range. Categorical variables will be summarized using counts and percentages.

7.9 STATISTICAL SOFTWARE

The statistical software package SAS® 9.4 or later will be used for all the data derivations, summarization, data listings and statistical analyses. Additional statistical software may be used for graphics or validation purposes as appropriate.

7.10 PERIODIC REVIEW OF CONTROLLER DATA

CGM and Omnipod 5 device data will be made available to Sponsor representatives for periodic reviews. Reviews of the controller data will be conducted to identify any anomalies and to confirm the algorithm appears to be functioning as expected. These reviews, including any findings, will be documented. Unless potential safety concerns are identified, the results of such reviews will not be shared with study sites or participants and thus, will not impact study endpoints. Should a potential safety concern be identified, sites may be notified as appropriate to ensure participant safety and measures may be taken to address the issue such as, but not limited to, changes to the protocol and/or device. Any resulting device deficiencies will be reported, if applicable. A brief summary of the controller data reviews will be included in the final clinical study report.

Insulet

8 **REFERENCES**

- [1] L. Fisher, D. Hessler, W. Polonsky, L. Strycker, U. Masharani and A. Peters, "Diabetes distress in adults with type 1 diabetes: Prevalence, incidence and change over time," J Diabetes Complications, vol. 30, no. 6, pp. 1123-8, 2016.
- [2] Y. Mouelhi, E. Jouve, C. Castelli and S. Gentile, "How is the minimal clinically important difference established in health-related quality of life instruments? Review of anchors and methods," *Health and Quality of Life Outcomes,* Vols. 18, 136, no. 136, pp. 1-17, 2020.
- [3] T. H. P. Draak, B. T. A. de Greef, C. G. Faber and I. S. J. Merkies, "The minimum clinically important difference: which direction to take," *Eur J Neurol*, vol. 26, no. 6, pp. 850-855, 2019.
